7.3 HANDLING OF MISSING DATA

For the primary efficacy endpoint which is continuous in nature, the use of a restricted maximum likelihood (REML)-based mixed model repeated measures (MMRM) approach, in the primary analysis, will ensure that missing data are handled implicitly, via a missing at random assumption, by the statistical model.

In order to check the robustness of the primary MCPMod analysis to missing data, a sensitivity analysis will be performed using adjusted multiple imputation. Non-monotone missing data will initially be multiply imputed as missing-at-random. For monotone missing data, a Jump to Reference method will then be implemented via a sequential regression MI approach. For such missing data, patients in the active treatment groups are assumed to lose any treatment effect with their missing observations and to then assume a trajectory similar to that of the placebo group. For each imputed complete dataset, an ANCOVA (Analysis of Covariance) model for Week 16 data analogous to the primary MMRM model will be used for the analysis. The results will be pooled using Rubin's rules and the primary MCPMod analysis will be repeated on the summarized outcomes. Further details on the procedure will be included in the TSAP.

For secondary efficacy endpoints of a binary nature, a Non Response Imputation (NRI) approach, will be applied to the missing visits up to Week 52 that is, imputing as a failure to achieve a response in the visits with missing endpoint score, however:

- If there are available data at the visits both before and after the visit with a missing outcome, then impute as a success only if both the preceding and the following measurement indicate success (that is, score of 1) and there is no use of rescue therapy for disease worsening within this imputation period;
- Otherwise, impute as a failure to achieve a response (i.e. no response imputation).

Multiple imputation will be used as a sensitivity analysis to handle missing secondary binary data. Detailed description of multiple imputation will be included in the TSAP.

With respect to safety evaluations, it is not planned to impute missing values.

7.4 RANDOMISATION

BI will arrange for the randomisation and the packaging and labelling of trial medication. The randomisation list will be generated using a validated system, which involves a pseudo-random number generator so that the resulting treatment will be both reproducible and non-predictable. The block size will be documented in the Clinical Trial Report. Access to the codes will be controlled and documented.

Stratification of the randomisation will be performed for Japan versus non-Japan.

Within each stratum, patients will be randomised in a 2:1:1:1:2 randomisation ratio to receive either placebo or one of four BI 655130 dose regimens (“high dose” regimen; “medium-high dose” regimen; “medium-low dose” regimen; “low dose” regimen). The randomisation will be done in blocks to achieve balanced allocation.

The process of randomisation is done via an IRT. Practical aspects of the treatment allocation process are detailed in [Section 4.1.3](#).

7.5 DETERMINATION OF SAMPLE SIZE

Calculations were performed using R Version 3.5.1.

The study is intended to show a benefit of BI 655130 over placebo in terms of the difference in % PPP ASI change at Week 16.

The aims of this study are two-fold. A first aim is to show a significant non-flat dose-response curve across the different doses and placebo. Additionally to that at least one modelled dose within the dose range considered should show a benefit of at least "Delta" % PPP ASI change compared to placebo. The probability of success of this trial is therefore defined as the probability to (1) obtain a significant test for non-flat dose-response curve and (2) to observe for at least one of the modelled doses an effect difference of at least delta compared to placebo.

The sample size calculation is based on an assumed maximum difference in % PPP ASI change of placebo vs. BI 655130 of 30%, as well as on the pre-specified models listed in [Section 7.2.2](#). The standardized deviation of the % PPP ASI change is assumed to be 35%.

For placebo, a fixed rate of -25% PPP ASI change at Week 16 will be considered. These estimates are derived from trial 1368.15 in PPP.

Using a total sample size of 140 evaluable patients (40, 20, 20, 20 and 40 for placebo and low to high dose regimes respectively), the probability for a successful trial (as defined above) was estimated using simulations. For each dose group, samples of the required size were drawn from a normal distribution. Values smaller than -100% (which corresponds to complete recovery of a patient) were set to -100%. The expected values of the original normal distribution were chosen such that the expected dose group means after truncation correspond to the model assumptions. In the following, the reported dose means will always refer to dose means after truncation. The standard deviation of the untruncated normal distribution was set to 35% for all simulations. This will result in slightly reduced standard deviations after truncation (of approx. 30% for the highest dose group).

Based on these assumptions, the success probability under a delta of 25% (i.e. non-flat curve achieved, and at least one BI 655130 dose shows a difference to placebo of at least 25%) is approximately 77% when assuming a linear dose response curve (i.e. -25, -40, -44, -51 and -55% PPP ASI change for placebo and low to high dose regimens, respectively). Assuming one of the other dose response curves listed in [Section 7.2.2](#) the success probability is between 79% and 84%. For a delta of 20% the respective success probabilities are between 93 and 96%.

If the difference between placebo and active doses is low, i.e. 10% (which is assumed to be clinically not relevant) the success probability is approximately 2% and 9% for a delta of 25% and 20%, respectively (assuming a linear dose response curve). In the case that there is no treatment benefit, the false positive probability is limited by the α -level for the significance testing of the non-flat dose-response curve of 5% (one-sided). Additionally, this probability is further reduced by requesting an effect of at least delta. Thereby, the probability of a false decision for a non-effective drug is reduced to less than 1%.

The following Table 7.5: 1 provides success probabilities under different scenarios (i.e. different treatment effects and dose-response curves).

Table 7.5: 1 Probability of multiplicity-adjusted success probability given expected % change in PPP ASI at week 16 and a total sample size of 140 patients (with 40/20/20/20/40 per dose group) based on MCPMod nominal alpha-level of 5% (one-sided) and additional treatment effect threshold (Delta).

(Assumed) True Model	Expected % change in PPP ASI (in %)					Exp. max. Response Difference	Delta	Multiplicity adjusted Success probability*
	Placebo	Low dose BI	Medium-low dose BI	Medium-high dose BI	High dose BI			
Linear30	-25	-40	-44	-51	-55	30	25	77,1%
Emax30	-25	-51	-52	-54	-55	30	25	80,7%
Exp30	-25	-29	-33	-42	-55	30	25	79,0%
Logistic30	-25	-31	-43	-54	-55	30	25	84,4%

Table 7.5: 1 (cont.) Probability of multiplicity-adjusted success probability given expected % change in PPP ASI at week 16 and a total sample size of 140 patients (with 40/20/20/20/40 per dose group) based on MCPMod nominal alpha-level of 5% (one-sided) and additional treatment effect threshold (Delta).

(Assumed) True Model	Expected % change in PPP ASI (in %)					Exp. max. Response Difference	Delta	Multiplicity adjusted Success probability*
	Placebo	Low dose BI	Medium-low dose BI	Medium-high dose BI	High dose BI			
SigEmax30	-25	-28	-37	-51	-55	30	25	83,6%
Linear40	-25	-45	-51	-59	-65	40	25	98,2%
Linear0	-25	-25	-25	-25	-25	0	25	<0,1%
Linear10	-25	-30	-31	-34	-35	10	25	1,8%
Linear30	-25	-40	-44	-51	-55	30	20	93,2%
Emax30	-25	-51	-52	-54	-55	30	20	94,6%
Exp30	-25	-29	-33	-42	-55	30	20	93,8%
Logistic30	-25	-31	-43	-54	-55	30	20	95,8%
SigEmax30	-25	-28	-37	-51	-55	30	20	95,5%
Linear40	-25	-45	-51	-59	-65	40	20	99,8%
Linear0	-25	-25	-25	-25	-35	0	20	0,4%
Linear10	-25	-30	-31	-34	-25	10	20	8,7%

*Success probabilities under different efficacy assumptions for the defined success criteria of 1) Significant non-flat dose-response achieved based on at least one of the candidate set models AND 2) Treatment benefit of at least 'delta' compared to placebo for at least one modelled dose within the considered dose range. Success probabilities have been calculated using R Version 3.5.1 based on simulations (10000 simulations per scenario). Thereby the calculations for the MCPMod step have been performed using DoseFinding R-package 0.9-16 [R15-2001].

“Linear30: Main scenario reflecting the assumption of maximum effect difference of 30% compared to placebo assuming a linear dose-response curve as defined in [Section 7.2.2](#).

“Emax30: Alternative scenario reflecting the assumption of maximum effect difference of 30% compared to placebo assuming an Emax dose-response curve as defined in [Section 7.2.2](#).

“Exp30: Alternative scenario reflecting the assumption of maximum effect difference of 30% compared to placebo assuming an exponential dose-response curve as defined in [Section 7.2.2](#).

“Logistic30: Alternative scenario reflecting the assumption of maximum effect difference of 30% compared to placebo assuming a logistic dose-response curve as defined in [Section 7.2.2](#).

“SigEmax30: Alternative scenario reflecting the assumption of maximum effect difference of 30% compared to placebo assuming a sigmoid dose-response curve as defined in [Section 7.2.2](#).

“Linear40: Alternative scenario reflecting the assumption of a higher maximum effect difference of 40% compared to placebo assuming a linear dose-response curve.

“Linear0: Alternative scenario reflecting the assumption of no difference compared to placebo assuming a linear dose-response curve.

“Linear10: Alternative scenario reflecting the assumption a clinically not relevant maximum effect difference of 10% compared to placebo assuming a linear dose-response curve.

8. INFORMED CONSENT, TRIAL RECORDS, DATA PROTECTION, PUBLICATION POLICY, AND ADMINISTRATIVE STRUCTURE

The trial will be carried out in compliance with the protocol, the ethical principles laid down in the Declaration of Helsinki, in accordance with the ICH Harmonized Guideline for Good Clinical Practice (GCP), relevant BI Standard Operating Procedures (SOPs), the EU regulation 536/2014, the Japanese GCP regulations (Ministry of Health and Welfare Ordinance No. 28, March 27, 1997) and other relevant regulations. Investigators and site staff must adhere to these principles. Deviation from the protocol, the principles of ICH GCP or applicable regulations as will be treated as “protocol deviation”.

Standard medical care (prophylactic, diagnostic and therapeutic procedures) remains the responsibility of the treating physician of the patient.

The investigator will inform the sponsor immediately of any urgent safety measures taken to protect the trial patients against any immediate hazard, as well as of any serious breaches of the protocol or of ICH GCP.

The Boehringer Ingelheim transparency and publication policy can be found on the following web page: trials.boehringer-ingelheim.com. The rights of the investigator and of the sponsor with regard to publication of the results of this trial are described in the investigator contract. As a rule, no trial results should be published prior to finalisation of the Clinical Trial Report.

The certificate of insurance cover is made available to the investigator and the patients, and is stored in the ISF.

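### Do the exchanged high-dose means for Linear0 and Linear10 at delta = 20 in Protocol Table 7.5: 1 put the stated go probabilities in doubt?

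*Protocol*

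**What the plan says.** Table 7.5: 1 lists eight scenarios twice, once for each threshold. Each row gives five means (placebo, then low to high dose), the expected maximum difference from placebo, delta, and the success probability in per cent.

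- Delta = 20: "Linear0 -25 -25 -25 -25 -35 0 20 0,4" and "Linear10 -25 -30 -31 -34 -25 10 20 8,7".
- Delta = 25: "Linear0 -25 -25 -25 -25 -25 0 25 <0,1" and "Linear10 -25 -30 -31 -34 -35 10 25 1,8".
- Footnote to Linear0: "Alternative scenario reflecting the assumption of no difference compared to placebo assuming a linear dose-response curve".
- Footnote to Linear10: "Alternative scenario reflecting the assumption a clinically not relevant maximum effect difference of 10% compared to placebo".
- Section 7.5 prose, 10-point linear effect: "the success probability is approximately 2% and 9% for a delta of 25% and 20%, respectively".
- Section 7.5 prose, no effect: "the probability of a false decision for a non-effective drug is reduced to less than 1" (per cent).

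Section 7 of the protocol sets the proof-of-concept benefit at 20 points, so the delta = 20 block is the one that matches the decision rule.

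**The concern.** Linear0 and Linear10 are the only rows that show how often a drug with no effect, or with an effect too small to matter, would still pass at the 20-point threshold. As printed, neither row is consistent with itself. Linear0 has a 10-point effect at the high dose. Linear10 falls back to the placebo mean at the high dose, so it cannot be a linear curve.

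If the simulation had been run on the printed means, or the probabilities attached to the wrong rows, the false-go risk would be misreported. Taken literally, the Linear0 row says that a 10-point effect confined to the top dose leads to a go in 0.4% of trials, when the true figure is near 9%. Anyone repeating the simulation from the printed means would fail to match either row.

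**Working it through.** **1. Arithmetic on the rows as printed (delta = 20).** Difference from placebo = 25 minus the size of the dose-group reduction, with the sign reversed.

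- Linear0: 0, 0, 0, 35 - 25 = 10. The maximum is 10; the column says 0.
- Linear10: 5, 6, 9, 25 - 25 = 0. The maximum is 9, at the medium-high dose; the column says 10.

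Exchanging the two high-dose cells gives maxima of 0 and 10, as the column states.

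**2. What a linear curve requires.** The doses are redacted, but relative doses follow from the linear contrast in SAP Table 7.4: 2 (0.783, 0.049, -0.049, -0.196, -0.587) divided by n = 40, 20, 20, 20, 40: 0.019575, 0.00245, -0.00245, -0.0098, -0.014675. The distance of each from the placebo value, divided by the full range 0.03425, gives 0, 0.500, 0.643, 0.858, 1. A 10-point linear effect from -25 is then -25, -30.0, -31.4, -33.6, -35.0. Rounded, this is the delta = 25 row exactly.

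**3. Same scenario, other block.** Delta is a decision threshold and does not enter the data generation, so the means should be the same in both blocks. For the six other scenarios they are.

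**4. Hand check of the probabilities (high dose against placebo only, ignoring modelling and truncation).** SE = 35 × √(1/40 + 1/40) = 7.83.

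- True difference 0: P(observed ≥ 20) = 1 - Φ(20/7.83) = 0.53%.
- True difference 10: P(observed ≥ 20) = 1 - Φ(10/7.83) = 10.1%.

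These are close to the stated 0.4% and 8.7% under the row labels.

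**5. Simulation of the stated procedure.** Inputs from Section 7.5: SD 35 before truncation, values below -100 set to -100, means matched after truncation, n = 40/20/20/20/40. The test is the maximum of the five contrasts at one-sided 5% (critical value 1.94). Significant models are refitted and averaged with weights proportional to exp(-0.5·AIC). SAP Section 7.4 prints the exponent without the minus sign; the usual sign was used.

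Rows not in dispute, computed against stated: Linear30 at delta 20, 92.3% against 93.2%; SigEmax30 at delta 20, 95.3% against 95.5%; Linear40 at delta 20, 99.8% against 99.8%. The worst is Exp30 at delta 25, 75.3% against 79.0%.

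Rows in dispute (200,000 trials each):

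| Means | Delta 20 | Delta 25 |
|---|---|---|
| All -25 | 0.42% | 0.04% |
| -25, -30, -31, -34, -35 | 9.42% | 2.08% |
| -25, -25, -25, -25, -35 (Linear0 as printed at delta 20) | 8.82% | 1.79% |
| -25, -30, -31, -34, -25 (Linear10 as printed at delta 20) | 0.99% | 0.10% |

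The protocol states 0.4% and 8.7% at delta 20, and below 0.1% and 1.8% at delta 25. A separate run gave 0.45% and 9.45% for the intended means at delta 20, and 8.91% and 0.94% for the printed ones.

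**The case for a change.** The best case for a correction is that the contradiction is real, sits in the two rows that describe false-go risk at the operative threshold, and would take two cells to put right. On the text supplied, the contradiction stands, and so does its direction.

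The harm does not follow. To be misled, a reader would have to ignore the row label, the difference column, the footnote, the other block and the prose, all of which agree. Nothing later in the plan takes these cells as input: the contrasts and models come from the candidate shapes in Protocol Section 7.2.2, and the decision rule from Section 7.

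Three limits apply:

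- The simulation alone does not show which column was exchanged. Had the probabilities been swapped instead, the printed Linear0 means would give 8.82% against 8.7%, a closer match than 9.42%. The labels, footnotes and prose settle that the means moved.
- The intended Linear10 means give about 0.7 points more than the stated 8.7%. With the protocol's 10,000 runs the Monte Carlo SE is √(0.087 × 0.913/10,000) = 0.28 points, so the gap exceeds simulation noise. The original fitting settings are not shown. The stated figures are consistent with the intended means, not reproduced exactly.
- The table crosses a page break and was read by a program, so the exchange may not be in the source PDF. Every other cell in the two rows aligns, so this is possible but not shown.

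**Conclusion.** This is a clerical slip and no change to the plan follows. Two high-dose cells at delta = 20 are exchanged: -25 belongs to Linear0 and -35 to Linear10. The stated 0.4% and 8.7% fit those means to within about 0.7 points, while the printed means miss by about 8 points each (8.82 - 0.4 = 8.4 and 8.7 - 0.99 = 7.7). The false-go statements in Section 7.5 (below 1% for no effect, about 9% for a 10-point effect at delta 20) hold. Correcting the cells would alter no probability, sample size, threshold or analysis, and nothing the trial could conclude.

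The identification of the slip rests on the documents' own labels, footnotes and prose. The simulation supports it, assuming relative doses recovered from the SAP contrasts and conventional AIC weights. In the separate run, using the single best-AIC model instead of averaging gives 0.52% and 9.91% for the intended means, so the conclusion does not hang on the averaging method.

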8.1 TRIAL APPROVAL, PATIENT INFORMATION, INFORMED CONSENT

This trial will be initiated only after all required legal documentation has been reviewed and approved by the respective Institutional Review Board (IRB / Independent Ethics Committee (IEC and competent authority (CA) according to national and international regulations. The same applies for the implementation of changes introduced by amendments.

Prior to patient participation in the trial, written informed consent must be obtained from each patient (or the patient’s legally accepted representative) according to ICH-GCP and to the regulatory and legal requirements of the participating country. Each signature must be personally dated by each signatory and the informed consent and any additional patient-information form retained by the investigator as part of the trial records. A signed copy of the informed consent and any additional patient information must be given to each patient or the patient’s legally accepted representative.”

The investigator or delegate must give a full explanation to trial patients based on the patient information form. A language understandable to the patient should be chosen, technical terms and expressions avoided, if possible.

The patient must be given sufficient time to consider participation in the trial. The investigator or delegate obtains written consent of the patient’s own free will with the

informed consent form after confirming that the patient understands the contents. The investigator or [REDACTED] delegate must sign (or place a seal on) and date the informed consent form. If a trial collaborator has given a supplementary explanation, the trial collaborator also signs (or places a seal on) and dates the informed consent.

Re-consenting may become necessary when new relevant information becomes available and should be conducted according to the sponsor's instructions.

The consent and re-consenting process should be properly documented in the source documentation.

8.2 DATA QUALITY ASSURANCE

A risk-based approach is used for trial quality management. It is initiated by the assessment of critical data and processes for trial subject protection and reliability of the results as well as identification and assessment of associated risks. An Integrated Quality and Risk Management Plan documents the rationale and strategies for risk management during trial conduct including monitoring approaches, vendor management and other processes focusing on areas of greatest risk.

Continuous risk review and assessment may lead to adjustments in trial conduct, trial design or monitoring approaches.

A quality assurance audit/inspection of this trial may be conducted by the sponsor, sponsor's designees, or by IRB / IEC or by regulatory authorities. The quality assurance auditor will have access to all medical records, the investigator's trial-related files and correspondence, and the informed consent documentation of this clinical trial.

8.3 RECORDS

CRFs for individual patients will be provided by the sponsor. See [Section 4.1.5.2](#) for rules about emergency code breaks. For drug accountability, refer to [Section 4.1.8](#).

8.3.1 Source documents

In accordance with regulatory requirements, the investigator should prepare and maintain adequate and accurate source documents and trial records that include all observations and other data pertinent to the investigation on each trial patient. Source data as well as reported data should follow the "ALCOA principles" and be attributable, legible, contemporaneous, original and accurate. Changes to the data should be traceable (audit trail).

Data reported on the CRF must be consistent with the source data or the discrepancies must be explained.

The current medical history of the patient may not be sufficient to confirm eligibility for the trial and the investigator may need to request previous medical histories and evidence of any diagnostic tests. In this case, the investigator must make at least one documented attempt to retrieve previous medical records. If this fails, a verbal history from the patient, documented in their medical records, would be acceptable.

Before providing any copy of patient's source documents to the sponsor the investigator must ensure that all patient identifiers (e.g. patient's name, initials, address, phone number, social security number) have properly been removed or redacted from any copy of the patients' source documents.

If the patient is not compliant with the protocol, any corrective action e.g. re-training must be documented in the patient file.

For the CRF, data must be derived from source documents, for example:

- Patient identification: gender, year of birth (in accordance with local laws and regulations)
- Patient participation in the trial (substance, trial number, patient number, date patient was informed)
- Dates of patient's visits, including dispensing of trial medication
- Medical history (including trial indication and concomitant diseases, if applicable)
- Medication history
- Adverse events and outcome events (onset date (mandatory), and end date (if available))
- Serious adverse events (onset date (mandatory), and end date (if available))
- Concomitant therapy (start date, changes)
- Originals or copies of laboratory results and other imaging or testing results, with proper documented medical evaluation (in validated electronic format, if available)
- Completion of patient's participation in the trial" (end date; in case of premature discontinuation document the reason for it).
- Prior to allocation of a patient to a treatment into a clinical trial, there must be documented evidence in the source data (e.g. medical records) that the trial participant meets all inclusion criteria and does not meet any exclusion criteria. The absence of records (either medical records, verbal documented feedback of the patient or testing conducted specific for a protocol) to support inclusion/exclusion criteria does not make the patient eligible for the clinical trial.

